- 2. Our Innovative Study Approaches.** Within the right hand column of **Table 1**, we describe our innovative approaches designed to directly address gaps and reduce HTN disparities. In summary, our practice-based collaborative care team intervention, which is based upon the chronic care model (CCM),⁹² is pragmatic in that we will utilize existing staff infrastructure. Incorporation of subspecialist advice into the patient care plan for minority and socioeconomically disadvantaged patients as part of a stepped care approach is also a highly innovative strategy to address access barriers. The CCM is an effective approach to successfully manage patients with HTN, CVD and multiple co-morbidities, such as diabetes and depression^{42,93-96} but its use to reduce health disparities has been limited. The inclusion

of a community-based contextualized care intervention delivered by a CHW in the CCM is also novel. We will rigorously test the added benefit of a stepped care approach based on patient attainment of BP control. This approach includes either specialist consultation; a community-based component that engages patients' families and social networks; or both. Further, we will actively engage stakeholders to ensure that these approaches are achievable, sustainable, and scalable to other settings.

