5. **Employment of risk-stratified CC protocols.** The experimental intervention is implemented at half of the practices (n=15). This multilevel intervention includes the practice-based CC team with the option of stepping patients up (if their SBP remains ≥ 140 and/or DBP ≥ 90 after 3 months or 1 month in extenuating circumstances) to either obtain subspecialist consultation or to see a CHW. The CHW is an integrated member of the team and supports patients in reaching their self-management goals; helps patients address social and environmental barriers to engaging in care through outreach and navigation services; and engages, activates, and empowers patients and their support system to participate in the care process. After three additional months (or one month in extenuating circumstances), if a patient's BP continues to be uncontrolled or becomes uncontrolled, the CC team has the option of stepping the patient up again (adding either subspecialist consultation or CHW, as guided by the protocol). Thus patients in CC/Stepped care can receive CC only; CC+CHW; CC+Specialist; or CC+CHW+Specialist care.

The CM may deploy a CHW prior to one month if the patient is willing to work with a CHW AND at least one of the following conditions is met: no-show or difficult to engage patient; cardiac event in the last 12 months, with no follow-up appointment; inability to perform activities of daily living with no resources; no access to transportation; utility shut offs; food insecurity; domestic violence; poor/unstable housing; special request from the patient and/or the PCP.

6. **Reassessment at determined intervals or milestones.** Patients in CC/Stepped Care are reassessed per protocols based on their levels of BP and CVD risk factor control, weekly, biweekly, or monthly, until goals are attained.

B. Intervention approach: In UH2, our intervention was a stakeholder engagement process to plan and test recruitment for the trial. In UH3, we are conducting a two arm, prospective cluster-randomized trial and study of multi-level factors affecting implementation, quality improvement & disparities.

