D. Care Manager (CM) Roles and Responsibilities: The overarching role of the care manager (CM) is to spearhead organizing the delivery of care and appropriate interventions to the patient. The CM is the chief point-of-contact for the care team and for patients enrolled in the trial. He/she determines, using evidence-based protocols, when to enlist the support of other members of the care team and deploy them to deliver the protocols forming the crux of needed interventions. This is accomplished, in part, by administering an assessment developed to cover the NCQA key behavioral and psychosocial domains, which elucidates patients' clinical and social needs. The CM uses the results of the assessment to develop care plans with patients and allocate other care team resources in accordance with patients' priorities and needs. The CM monitors all aspects of each patient's progress toward achieving improved cardiovascular health outcomes and disease self-management, with a primary focus on medical management of HTN, CHD, diabetes, hyperlipidemia, depression, and tobacco cessation. To address the patient's psychosocial, behavioral, and mental health needs related to these conditions, the CM (or another behavioral health specialist, if available at the practice) provides counseling for health behavior change as well as psychosocial stressors and trauma (such as financial, job/non-job conflicts, relationship stressors, and community stressors). The CM employs psychosocial, behavioral, and mental health services protocols whenever the patient screens positive for depression (PHQ-8 \geq 5); is a current smoker and is either contemplative or ready to quit smoking in the next 30 days; and if the patient stress rating is >5 on the baseline patient needs assessment. If stressors remain high after 3 months of the basic CC intervention, the team will step the patient up to working with a CHW, and if these stressors contribute to depression or anxiety, the CM will step the patient up to consultation from the psychiatrist in the subspecialist core. If the patient's HTN or other conditions remain uncontrolled at 6 months, the CC team has a second opportunity to step up the patient's care to specialist consultation, CHW or both. For both CHW and specialist consultation, exceptions may be made to the timing of the initial step-up by special request from the patient and/or PCP, or for extenuating circumstances found to preclude successful achievement and management of BP control. Such circumstances include immobility, housing, transportation, utilities, and poor social/caregiver support. For specialist consultation, circumstances include poor disease control despite patient reports of adherence to several optimized regimens, and conflicting treatment recommendations for different conditions. Factors guiding the decision to step a patient up to a CHW, a specialist, or both are further elaborated in this document.

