Section 6C: Interventions Description: Community Health Worker

A. Background: Community Health Workers (CHWs) are crucial members of the clinic care teams. Their main **purpose** is to support patient participants' BP control by (1) educating participants on how to manage their own BP through self-monitoring and practicing healthy self-management behaviors (e.g., diet and exercise); (2) reinforcing participants' positive BP self-management behaviors through repeated follow up encounters (i.e., by telephone or in person); and (3) helping participants liaise with existing clinical and administrative services. CHWs also support participants by making them aware of community resources (e.g., local grocery stores, safe exercise venues) they can use to support their BP management. CHWs **engage with participants** through home visits, telephone contacts, and in-person visits at their practices on the day of their primary care appointments. The form of CHW engagement is flexible, participant-centered, and varies based on participants' stated preferences.

1. **Hiring and training.** Initially, we envisioned that the CHWs would be hired and trained by our research team; however, in response to feedback from our stakeholders, and for the purposes of sustainability, we have partnered with community-based organizations (CBOs) and payers to assist with hiring CHWs, as well as initial and ongoing training. Our approach depended on the desires expressed by each practice's leadership, and we worked collaboratively with all relevant entities to ensure that the hiring and deployment of CHWs was consistent with what the practices need. For practices that already had CHWs or wish to introduce them into their practices, we provided the requisite training to support their implementation of appropriate interventions for our study population. For practices that elected to have CHWs hired and placed by an outside CBO, we worked with both the practice leadership and the CBOs for hiring and training.

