| Support patient adherence to disease self-management behaviors and communication with providers | 
 - Engage, activate, and empower patients and their family members by: 
 o Working with patients to identify and address barriers to adherence to antihypertensive regimens o Providing ongoing support and encouragement o Facilitating identification of challenges o Coaching patients to disclose concerns to healthcare team o Building skills in asking questions o Discussing treatment options o Helping them learn to make joint decisions regarding treatment options o Overcoming common communication barriers - Address competing family priorities and needs - Assess and reinforce patient’s and family members’ pro-adherence beliefs and behaviors - Assess and reinforce patient’s and family members’ communication skills around disease-related needs and goals |

C. Patient Assessment and Longitudinal Engagement

1. Patient Assessment

a. Initial patient assessment

- i. CHWs participate in the initial assessment alongside the Care Manager, in order to establish rapport with patient and help patient to become familiar with members of the clinic care team
 - a) Care Manager determines whether or not patient requires immediate assistance from CHW
 - b) At 3 months, the CM deploys the CHW as a step-up intervention if **at least one** of the following conditions are met:
 - i. Patient’s BP or other conditions remain uncontrolled

- ii. Patient continues to experience barriers to care and food insecurity
 - iii. Patient is willing to work with a CHW
- c) For both CHW and specialist consultation, exceptions may be made to the timing of the initial referral by special request from the patient and/or PCP, or for extenuating circumstances found to prevent successful achievement and management of BP control. In these situations, referral may occur immediately or at 1 month instead of at 3 months.
- d) The CM may make an immediate referral to a CHW if The CM may deploy a CHW prior to one month if the patient is willing to work with a CHW AND at least one of the following conditions is met:
- i. Cardiac event in the last 12 months, with no follow-up appointment
 - ii. Inability to perform activities of daily living with no resources
 - iii. No access to transportation
 - iv. Utility shut offs
 - v. Food insecurity
 - vi. Domestic violence
 - vii. Poor/unstable housing

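### As written, the 3-month rule lets willingness alone trigger a CHW step-up, and the planned analysis of CM and CHW contacts can support description only

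*Combined protocol and SAP*

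**What the plan says.** The step-up to a CHW is described in several places.

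- **Section 6C, Community Health Worker, C.1.a, item b (3 months):** "At 3 months, the CM deploys the CHW as a step-up intervention if at least one of the following conditions are met". The conditions are (i) BP or other conditions still uncontrolled, (ii) continuing barriers to care and food insecurity, and (iii) "Patient is willing to work with a CHW".
- **The same list, item d, and Section 6A item 5 (early deployment):** the CM is allowed to send one "prior to one month if the patient is willing to work with a CHW AND at least one of the following conditions is met".
- **Section 6A item 5 (3 months):** the CC team works "with the option of stepping patients up (if their SBP remains ≥ 140 and/or DBP ≥ 90 after 3 months", or after 1 month in extenuating circumstances. The next scheduled step also depends on BP only.
- **Section 6C, Collaborative Care Intervention, D:** "If stressors remain high after 3 months of the basic CC intervention, the team will step the patient up to working with a CHW". Further on, if a patient's "HTN or other conditions remain uncontrolled at 6 months, the CC team has a second opportunity to step up" care.
- **Section 1C.2 (background):** "We will rigorously test the added benefit of a stepped care approach based on patient attainment of BP control".
- **Section 6C, Community Health Worker, A:** "The form of CHW engagement is flexible, participant-centered, and varies based on" what participants say they prefer.

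Section 8 (Subgroup and Exploratory Analyses) plans an exploratory analysis within the CC/Stepped Care arm. It is to find which parts of the intervention, such as numbers of CM and CHW contacts, did more for BP control and systolic BP, and whether there is a dose effect. It names no adjustment specific to that analysis.

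**The concern.** Item b is the detailed rule for who receives a CHW at the scheduled review. Because its conditions are alternatives, willingness is sufficient on its own and is never necessary. Anyone describing or replicating the intervention from this text would take away a rule that hardly selects patients, and one that disagrees with the framework section at the same time point.

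The second matter does not depend on which wording is right. Patients with a CHW are there because BP was uncontrolled, because another trigger was present, or because they were willing, and these features can also predict BP at 12 months. A comparison by number of contacts mixes them with any effect of the CHW, so a statement about which component worked better would not be supported.

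**Working it through.** The plan gives no figure to reproduce here. The check has two parts.

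**1. The rules compared as logic.** Take four yes/no states at 3 months: BP uncontrolled (B), another condition uncontrolled (O), barriers or food insecurity (R) and willing (W). That makes 2⁴ = 16 combinations. They are logical states, not patients.

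- Item b as written, B or O or R or W: 16 − 1 = 15 qualify.
- Willing and at least one of B, O, R: 2³ − 1 = 7 qualify.
- Section 6A item 5, B only: 8 qualify.

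Item b exceeds the willing-and-trigger rule by 15 − 7 = 8 states: 1 willing with no trigger, and 7 with a trigger but unwilling. It exceeds the BP-only step by 15 − 8 = 7 states: 1 with willingness alone, and 6 with controlled BP and another trigger (3 patterns of O and R, times 2 states of W). The BP-only step is silent on willingness, so the two rules agree on an unwilling patient with uncontrolled BP. For that patient the mismatch is with the form of item d. The stressor trigger in the Care Manager section appears neither in item b nor in the scheduled steps of Section 6A item 5.

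**2. What the contact analysis could show if the CHW did nothing.** The SBP standard deviation of 19.5 mm Hg comes from Section 8 (Power calculation). All other inputs are assumptions:

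- proportion uncontrolled at month 3: 0.3 or 0.5
- proportion willing: 0.5, 0.7 or 0.9, independent of 3-month BP
- correlation r between 3- and 12-month SBP: 0.3 or 0.5
- 12-month SBP lower in willing patients by δ = 2 or 5 mm Hg

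This gives 2 × 3 × 2 × 2 = 24 scenarios of 378,000 simulated patients, without clustering. The model is S12 = m + r(S3 − m) + 19.5√(1 − r²)·e − δW. Here m is the mean that gives the chosen proportion with S3 ≥ 140, e is standard normal, and control means S12 < 140. The CHW effect is zero, so the correct odds ratio for contact is 1.

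| Who has CHW contact | Adjusted for | Odds ratio, range |
|---|---|---|
| Uncontrolled and willing | nothing | 0.26–0.79 |
| Uncontrolled and willing | 3-month SBP | 1.07–1.54 |
| Uncontrolled and willing | SBP, willingness | 0.96–1.06 |
| Willing, and uncontrolled or non-BP trigger (in 30%, +3 mm Hg at 12 months) | SBP, willingness | 0.80–0.87 |
| Same | SBP, willingness, trigger | 0.96–1.04 |
| Item b read literally, refusers untreated | 3-month SBP | 1.19–1.67 |

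In the last row contact and willingness are the same variable, so willingness cannot be adjusted for.

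The near-null third row depends on willingness lowering SBP equally in controlled and uncontrolled patients. In that row every willing uncontrolled patient has contact, so the willingness effect is learned only from controlled patients. With 2 mm Hg in controlled and 5 mm Hg in uncontrolled patients, the same adjusted odds ratio is 1.28–1.42. With the two reversed it is 0.73–0.82. The fully adjusted model can therefore show either false benefit or false harm. Simulation error is a few hundredths at the limits.

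**The case against.** - **Early rule.** It governs a different time, and its list ends with a special request from the patient or PCP. A willing patient who asks can therefore qualify early with controlled BP and no barrier. This stands: the contrast with item d is one of form, and the direct conflict is with Section 6A item 5 at 3 months. Section 1C.2 is background and not a deployment rule.
- **Section 6A item 5 as overview.** It speaks of an option, Section 6B (Arm 2) refers by page to the CHW and specialist descriptions, and the Care Manager section says the step-up factors are elaborated elsewhere. This stands too: its missing non-BP triggers are ordinary overview drafting, and a cross-reference would be tidying.
- **Manuals.** The CM and CHW manuals are not in the documents. A reader might infer that CHWs were actually assigned on willingness alone. The documents do not show that; they show only that the written rules differ. Rewording item b without checking could misdescribe what was delivered.
- **Flexibility.** Section 3F.2 leaves content, location and frequency of contacts to patient needs. That does not settle who is stepped up.
- **Simulation.** It compares contact with no contact, while Section 8 speaks of the number of contacts, and almost all inputs are assumed. Section 8 allows appropriate covariates in general, so adjustment is unspecified and not excluded. All of this stands, and the odds ratios are illustrations only.
- **Records.** The standard form that asks for the reason for consultation belongs to specialist referral. The logs in Section 9 cover step-ups and issues discussed, and no willingness field is named. Patients never offered a CHW may never have been asked. This limits how far adjustment can go.

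**Conclusion.** The point holds on the text. Item b makes willingness a sufficient trigger, which conflicts with the BP-based step at the same 3 months and with the willing-and-condition form used for early deployment. By logical states the rule admits 15 of 16, where 7 would qualify if willingness were required.

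The contact analysis is confounded by indication and by willingness under any of these rules, so correcting the wording does not rescue it. The simulations show that the bias can run in either direction and can survive adjustment. They rest on assumed inputs apart from the 19.5 mm Hg and do not estimate the bias in this trial.

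Two stronger readings are not supported. A reader might infer that the main result is compromised. It is not: the arms are compared by intention to treat, and the power calculation does not use the step-up rule. A reader might also infer that adjusting for BP, trigger and willingness would make the contact analysis causal. That needs an equal willingness effect in controlled and uncontrolled patients, for which the documents give no evidence.

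**What to change.** 1. **Item b.** After checking the CM and CHW manuals, reword it so that at 3 months the CM deploys a CHW if the patient is willing and at least one of these holds: BP or other study conditions remain uncontrolled; barriers to care or food insecurity continue; stressors remain high (from the Care Manager section). If a different rule was delivered, state that rule instead. A cross-reference from Section 6A item 5 to Section 6C is optional.
2. **Section 8, analysis of CM and CHW contacts.** Report it as descriptive, with no conclusion about which components did better. Show it adjusted for BP at the step-up review, and for trigger and willingness only where existing records hold them. State that residual confounding remains, and why.

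The cost is one wording edit, a check against the manuals, whatever record abstraction proves possible, and a weaker claim for one exploratory analysis. The Coaching Calls text puts all interventions in place at all health systems before the April 2019 change in call frequency. Most scheduled reviews have therefore probably passed, and the information would have to come from records already made.
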